5.6 Rescue Medications & Supportive Care

5.6.1 Supportive Care Guidelines for Pembrolizumab

Subjects should receive appropriate supportive care measures as deemed necessary by the treating investigator. Suggested supportive care measures for the management of AEs with potential immunologic etiology are outlined. Where appropriate, these guidelines include the use of oral or intravenous treatment with corticosteroids as well as additional anti-inflammatory agents if symptoms do not improve with administration of corticosteroids. Note that several courses of steroid tapering may be necessary as symptoms may worsen when the

steroid dose is decreased. For each disorder, attempts should be made to rule out other causes such as metastatic disease or bacterial or viral infection, which might require additional supportive care. The treatment guidelines are intended to be applied when the investigator determines the events to be related to pembrolizumab.

Note: Refer to Section 5.2.1 for dose modification.

It may be necessary to perform conditional procedures such as bronchoscopy, endoscopy, or skin photography as part of evaluation of the event.

- **Pneumonitis:**
 - For **Grade 2 events**, treat with systemic corticosteroids. When symptoms improve to Grade 1 or less, steroid taper should be started and continued over no less than 4 weeks.
 - For **Grade 3-4 events**, immediately treat with intravenous steroids. Administer additional anti-inflammatory measures, as needed.
 - Add prophylactic antibiotics for opportunistic infections in the case of prolonged steroid administration.
- **Diarrhea/Colitis:**

Subjects should be carefully monitored for signs and symptoms of enterocolitis (such as diarrhea, abdominal pain, blood or mucus in stool, with or without fever) and of bowel perforation (such as peritoneal signs and ileus).

 - All subjects who experience diarrhea/colitis should be advised to drink liberal quantities of clear fluids. If sufficient oral fluid intake is not feasible, fluid and electrolytes should be substituted via IV infusion. For Grade 2 or higher diarrhea, consider GI consultation and endoscopy to confirm or rule out colitis.
 - For **Grade 2 diarrhea/colitis** that persists greater than 3 days, administer oral corticosteroids.
 - For **Grade 3 or 4 diarrhea/colitis** that persists > 1 week, treat with intravenous steroids followed by high-dose oral steroids.
 - When symptoms improve to Grade 1 or less, steroid taper should be started and continued over no less than 4 weeks.
- **Type 1 diabetes mellitus** (if new onset, including diabetic ketoacidosis [DKA]) or **≥Grade 3 Hyperglycemia**, if associated with ketosis (ketonuria) or metabolic acidosis (DKA)
 - For **T1DM or Grade 3-4 Hyperglycemia**
 - Insulin replacement therapy is recommended for Type I diabetes mellitus and for Grade 3-4 hyperglycemia associated with metabolic acidosis or ketonuria.
 - Evaluate patients with serum glucose and a metabolic panel, urine ketones, glycosylated hemoglobin, and C-peptide.

- **Hypophysitis:**

- For **Grade 2** events, treat with corticosteroids. When symptoms improve to Grade 1 or less, steroid taper should be started and continued over no less than 4 weeks. Replacement of appropriate hormones may be required as the steroid dose is tapered.
- For **Grade 3-4** events, treat with an initial dose of IV corticosteroids followed by oral corticosteroids. When symptoms improve to Grade 1 or less, steroid taper should be started and continued over no less than 4 weeks. Replacement of appropriate hormones may be required as the steroid dose is tapered.

- **Hyperthyroidism or Hypothyroidism:**

Thyroid disorders can occur at any time during treatment. Monitor patients for changes in thyroid function (at the start of treatment, periodically during treatment, and as indicated based on clinical evaluation) and for clinical signs and symptoms of thyroid disorders.

- **Grade 2** hyperthyroidism events (and **Grade 2-4** hypothyroidism):
 - In hyperthyroidism, nonselective beta-blockers (e.g. propranolol) are suggested as initial therapy.
 - In hypothyroidism, thyroid hormone replacement therapy, with levothyroxine or liothyroinine, is indicated per standard of care.
- **Grade 3-4** hyperthyroidism
 - Treat with an initial dose of IV corticosteroid followed by oral corticosteroids. When symptoms improve to Grade 1 or less, steroid taper should be started and continued over no less than 4 weeks. Replacement of appropriate hormones may be required as the steroid dose is tapered.

- **Hepatic:**

- For **Grade 2** events, monitor liver function tests more frequently until returned to baseline values (consider weekly).
 - Treat with IV or oral corticosteroids
- For **Grade 3-4** events, treat with intravenous corticosteroids for 24 to 48 hours.
- When symptoms improve to Grade 1 or less, a steroid taper should be started and continued over no less than 4 weeks.

- **Renal Failure or Nephritis:**

- For **Grade 2** events, treat with corticosteroids.
- For **Grade 3-4** events, treat with systemic corticosteroids.
- When symptoms improve to Grade 1 or less, steroid taper should be started and continued over no less than 4 weeks.

- **Management of Infusion Reactions:** Signs and symptoms usually develop during or shortly after drug infusion and generally resolve completely within 24 hours of completion of infusion.

Table 12 below shows treatment guidelines for subjects who experience an infusion reaction associated with administration of pembrolizumab (MK-3475).

Table 12 Infusion Reaction Treatment Guidelines

NCI CTCAE Grade	Treatment	Premedication at subsequent dosing
Grade 1 Mild reaction; infusion interruption not indicated; intervention not indicated	Increase monitoring of vital signs as medically indicated until the subject is deemed medically stable in the opinion of the investigator.	None
Grade 2 Requires infusion interruption but responds promptly to symptomatic treatment (e.g., antihistamines, NSAIDS, narcotics, IV fluids); prophylactic medications indicated for <=24 hrs.	
Stop Infusion and monitor symptoms. Additional appropriate medical therapy may include but is not limited to:
 
IV fluids Antihistamines NSAIDS Acetaminophen Narcotics
 
Increase monitoring of vital signs as medically indicated until the subject is deemed medically stable in the opinion of the investigator. If symptoms resolve within one hour of stopping drug infusion, the infusion may be restarted at 50% of the original infusion rate (e.g., from 100 mL/hr to 50 mL/hr). Otherwise dosing will be held until symptoms resolve and the subject should be premedicated for the next scheduled dose.
 
Subjects who develop Grade 2 toxicity despite adequate premedication should be permanently discontinued from further trial treatment administration.
	Subject may be premedicated 1.5h (\pm 30 minutes) prior to infusion of pembrolizumab (MK-3475) with: Diphenhydramine 50 mg po (or equivalent dose of antihistamine). Acetaminophen 500-1000 mg po (or equivalent dose of antipyretic).
Grades 3 or 4 Grade 3: Prolonged (i.e., not rapidly responsive to symptomatic medication and/or brief interruption of infusion); recurrence of symptoms following initial improvement; hospitalization indicated for other clinical sequelae (e.g., renal impairment, pulmonary infiltrates)	
Stop Infusion. Additional appropriate medical therapy may include but is not limited to:
 
IV fluids Antihistamines NSAIDS Acetaminophen Narcotics Oxygen Pressors Corticosteroids Epinephrine
 
Increase monitoring of vital signs as medically indicated until the subject is deemed medically stable in the opinion of the investigator. Hospitalization may be indicated.
	No subsequent dosing

NCI CTCAE Grade	Treatment	Premedication at subsequent dosing
Grade 4: Life-threatening; pressor or ventilatory support indicated	Subject is permanently discontinued from further trial treatment administration.	
Appropriate resuscitation equipment should be available in the room and a physician readily available during the period of drug administration.		

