5.2.1.2 Dose Modification (Escalation/Titration/Other)

The CTCAE version 4.0 (CTCAE 4.0) must be used to grade the severity of AEs. If appropriate, the Investigator may attribute each toxicity event to cisplatin or carboplatin, 5-FU, cetuximab or pembrolizumab alone in the combination arms and use a stepwise dose reduction according to [Table 3](#). If a dose reduction for toxicity occurs with any agent, the dose may not be re-escalated. Dose modifications are always based on the previous cycle.

Subjects can have 2 levels of dose reductions per agent to cisplatin, carboplatin, 5-FU, and cetuximab throughout the course of the study for toxicities as described in [Table 3](#). If further toxicity occurs or the criteria for resuming treatment are not met, the subject must be discontinued from that drug and continue to participate in the study. For pembrolizumab

toxicities refer to [Table 4](#), platinum toxicities refer to [Table 5](#) and [Table 6](#), 5-FU toxicities refer to [Table 7](#) and [Table 8](#), and cetuximab toxicities refer to [Table 9](#), [Table 10](#), and [Table 11](#). If a subject experiences several toxicities and there are conflicting recommendations, follow the most conservative dose adjustment recommended (dose reduction appropriate to the most severe toxicity).

Reduction or holding of one agent and not the other agents is appropriate if, in the opinion of the Investigator, the toxicity is clearly related to one of the study drugs. If, in the opinion of the Investigator, the toxicity is related to the combination of 2 agents, both drugs should be reduced or held according to recommended dose modifications. If the toxicity is related to the combination of 3 agents, all 3 agents should be reduced or held according to the recommended dose modifications. If one or more study agent(s) are held for toxicity, the schedule for restarting the agent(s) should correspond with the next treatment cycle once the toxicity has resolved according to the recommended guidelines. Subjects who require more than 2 levels of dose reductions as outlined in [Table 3](#) below to any particular component of the regimen for toxicities will have that agent discontinued.

Exceptional circumstances to following the dose modification tables below may be considered after consultation with the Sponsor.

Table 3 Dose Modifications for Trial Medications

	Dose level 0	Dose level -1	Dose level -2	Dose level -3

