5.2.1.2.1 Immune-Related Events and Dose Modification (Withhold, Treat, Discontinue)

Dose Modification and Toxicity Management for Immune-related AEs Associated with Pembrolizumab

AEs associated with pembrolizumab exposure may represent an immune-related response. These irAEs may occur shortly after the first dose or several months after the last dose of pembrolizumab treatment and may affect more than one body system simultaneously. Therefore, early recognition and initiation of treatment is critical to reduce complications. Based on existing clinical study data, most irAEs were reversible and could be managed with interruptions of pembrolizumab, administration of corticosteroids and/or other supportive care. For suspected irAEs, ensure adequate evaluation to confirm etiology or exclude other causes. Additional procedures or tests such as bronchoscopy, endoscopy, skin biopsy may be included as part of the evaluation. Based on the severity of irAEs, withhold or permanently discontinue pembrolizumab and administer corticosteroids.

Dose Modification and Toxicity Management Guidelines for irAEs associated with pembrolizumab monotherapy, coformulations, or IO combinations are provided in [Table 4](#).

Table 4 Dose Modification and Toxicity Management Guidelines for Immune-related Adverse Events Associated with Pembrolizumab Monotherapy, Coformulations or IO Combinations

General instructions:				
irAEs	Toxicity Grade (CTCAEv4.0)	Action With Pembrolizumab Monotherapy, Coformulations or IO Combinations	Corticosteroid and/or Other Therapies	Monitoring and Follow-up
Pneumonitis	Grade 2	Withhold	
 Administer corticosteroids (initial dose of 1-2 mg/kg prednisone or equivalent) followed by taper 	
 Monitor participants for signs and symptoms of pneumonitis Evaluate participants with suspected pneumonitis with radiographic imaging and initiate corticosteroid treatment Add prophylactic antibiotics for opportunistic infections
	Recurrent Grade 2 or Grade 3 or 4	Permanently discontinue		

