Diarrhea / Colitis	Grade 2 or 3	Withhold	
 Administer corticosteroids (initial dose of 1-2 mg/kg prednisone or equivalent) followed by taper 	
 Monitor participants for signs and symptoms of enterocolitis (ie, diarrhea, abdominal pain, blood or mucus in stool with or without fever) and of bowel perforation (ie, peritoneal signs and ileus) Participants with \geGrade 2 diarrhea suspecting colitis should consider GI consultation and performing endoscopy to rule out colitis Participants with diarrhea/colitis should be advised to drink liberal quantities of clear fluids. If sufficient oral fluid intake is not feasible, fluid and electrolytes should be substituted via IV infusion.
	Recurrent Grade 3 or Grade 4	Permanently discontinue		

irAEs	Toxicity Grade (CTCAEv4.0)	Action With Pembrolizumab Monotherapy, Coformulations or IO Combinations	Corticosteroid and/or Other Therapies	Monitoring and Follow-up
AST / ALT Elevation or Increased Bilirubin	Grade 2	Withhold	
 Administer corticosteroids (initial dose of 0.5-1 mg/kg prednisone or equivalent) followed by taper 	
 Monitor with liver function tests (consider weekly or more frequently until liver enzyme value returned to baseline or is stable)
	Grade 3 or 4	Permanently discontinue	
 Administer corticosteroids (initial dose of 1-2 mg/kg prednisone or equivalent) followed by taper 	
T1DM or Hyperglycemia	New onset T1DM or Grade 3 or 4 hyperglycemia associated with evidence of β -cell failure	Withhold ^a	
 Initiate insulin replacement therapy for participants with T1DM Administer anti-hyperglycemic in participants with hyperglycemia 	
 Monitor participants for hyperglycemia or other signs and symptoms of diabetes
Hypophysitis	Grade 2	Withhold	
 Administer corticosteroids and initiate hormonal replacements as clinically indicated 	
 Monitor for signs and symptoms of hypophysitis (including hypopituitarism and adrenal insufficiency)
	Grade 3 or 4	Withhold or permanently discontinue ^a		
Hyperthyroidism	Grade 2	Continue	
 Treat with non-selective beta-blockers (eg, propranolol) or thionamides as appropriate 	
 Monitor for signs and symptoms of thyroid disorders

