	Grade 3 or 4	Withhold or Permanently discontinue ^a		

irAEs	Toxicity Grade (CTCAEv4.0)	Action With Pembrolizumab Monotherapy, Coformulations or IO Combinations	Corticosteroid and/or Other Therapies	Monitoring and Follow-up
Hypothyroidism	Grade 2-4	Continue	
 Initiate thyroid replacement hormones (eg, levothyroxine or liothyronine) per standard of care 	
 Monitor for signs and symptoms of thyroid disorders
Nephritis and renal dysfunction	Grade 2	Withhold	
 Administer corticosteroids (prednisone 1-2 mg/kg or equivalent) followed by taper 	
 Monitor changes of renal function
	Grade 3 or 4	Permanently discontinue		
Myocarditis	Grade 1	Withhold	
 Based on severity of AE administer corticosteroids 	
 Ensure adequate evaluation to confirm etiology and/or exclude other causes
	Grade 2, 3 or 4	Permanently discontinue		
All Other irAEs	Persistent Grade 2	Withhold	
 Based on severity of AE administer corticosteroids 	
 Ensure adequate evaluation to confirm etiology or exclude other causes
	Grade 3	Withhold or discontinue ^b		
	Recurrent Grade 3 or Grade 4	Permanently discontinue		

AE(s)=adverse event(s); ALT= alanine aminotransferase; AST=aspartate aminotransferase; CTCAE=Common Terminology Criteria for Adverse Events; DRESS=Drug Rash with Eosinophilia and Systemic Symptom; GI=gastrointestinal; IO=immuno-oncology; ir=immune related; IV=intravenous; SJS=Stevens-Johnson Syndrome; T1DM=type 1 diabetes mellitus; TEN=Toxic Epidermal Necrolysis; ULN=upper limit of normal.

Note: Non-irAE will be managed as appropriate, following clinical practice recommendations.

^a The decision to withhold or permanently discontinue pembrolizumab monotherapy, coformulations or IO combinations is at the discretion of the investigator or treating physician. If control achieved or ≤ Grade 2, pembrolizumab monotherapy, coformulations or IO combinations may be resumed.

^b Events that require discontinuation include, but are not limited to: Guillain-Barre Syndrome, encephalitis, myelitis, DRESS, SJS, TEN and other clinically important irAEs (eg, vasculitis and sclerosing cholangitis).

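### Section 5.6.1 makes its suggested steroids for pembrolizumab-related diarrhea/colitis conditional on persistence; Table 4 sets no such condition for Grade 2 or 3

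*Combined protocol and SAP*

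**What the plan says.** Two parts of the protocol advise on steroids for immune-related diarrhea/colitis.

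Section 5.6.1 has one bullet for Grade 2, covering an event "that persists greater than 3 days, administer oral corticosteroids", and one for Grade 3 or 4, covering an event "that persists > 1 week, treat with intravenous steroids followed by high-dose oral steroids". The section presents its measures as suggestions left to the treating investigator's judgment, for use once the investigator has attributed the event to pembrolizumab.

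Section 5.2.1.2.1 introduces Table 4 as the place for both dose modification and toxicity management of immune-related events. Its introduction says: "Therefore, early recognition and initiation of treatment is critical to reduce complications". It then ties action to grade: "Based on the severity of irAEs, withhold or permanently discontinue pembrolizumab and administer corticosteroids". In the diarrhea/colitis row of Table 4, the line for Grade 2 or 3 reads: "Administer corticosteroids (initial dose of 1-2 mg/kg prednisone or equivalent) followed by taper".

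Sites are directed to both places. Sections 5.2.1.2 and 5.2.1.2.1 point to Table 4. Section 7.1.2.1 (Adverse Event Monitoring) points to 5.6.1 for identifying, evaluating and managing potential immune-related events, and does not mention Table 4.

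**The concern.** For the same event, one section makes steroids depend on how long the diarrhea has lasted and the other makes them depend on grade alone. A site that goes from 7.1.2.1 to 5.6.1 and applies the bullet as written would hold back steroids in Grade 3 colitis until more than a week had passed. A site working from Table 4 has no reason to wait.

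What is at stake is subject safety and consistency of toxicity management between sites. No efficacy endpoint, estimate or test is involved.

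**Working it through.** The plan states no figure to reproduce. The check is a comparison of the texts, followed by simple date arithmetic on how many subjects could be exposed.

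**The texts side by side**

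| Grade | Section 5.6.1 | Section 5.2.1.2.1 and Table 4 |
|---|---|---|
| 2 | Oral steroids if lasting more than 3 days | 1-2 mg/kg prednisone or equivalent, then taper; no duration condition |
| 3 | Intravenous, then high-dose oral steroids if lasting more than 1 week | Same instruction as Grade 2; no duration condition |
| 4 | Same bullet as Grade 3 | Steroid cell not readable; only the general introduction applies |

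For Grades 2 and 3 the contrast is direct. For Grade 4 (and recurrent Grade 3, which shares its line) the steroid cell is blank in the text reviewed. The comparison there rests only on the introduction, which sets no start time for any particular event.

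**Does Table 4 leave persistence unstated as a matter of style?** Not everywhere. Its catch-all row for other immune-related events starts at "Persistent Grade 2". The diarrhea/colitis row carries no such qualifier.

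**Is a waiting condition usual within 5.6.1?** Graded bullets advising steroids, infusion reactions excluded: pneumonitis 2, diarrhea/colitis 2, hypophysitis 2, hyperthyroidism 1, hepatic 2, renal 2. The total is 2 + 2 + 2 + 1 + 2 + 2 = 11. Two of the 11 carry a persistence condition, both for diarrhea/colitis; the other 9 do not, and Grade 3-4 pneumonitis is to be treated at once. This is context only: different organ toxicities may warrant different advice.

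**Does the wait simply allow time for work-up?** Section 5.6.1 does ask sites to rule out other causes. But its treatment advice applies once the event is judged related to pembrolizumab, so the condition still operates after attribution.

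**Do the nearby rules settle it?** The note in 5.6.1 refers to Section 5.2.1 for dose modification only. The instruction in 5.2.1.2 to take the most conservative course covers dose adjustments when several toxicities conflict. Neither addresses when steroids start.

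**How many subjects could be exposed?** The documents give no count, so only a window can be estimated.
- Planned enrollment of 21 months (Section 8.2.7) plus the 24-month cap on pembrolizumab (Section 5.8.1) gives 21 + 24 = 45 months from the first subject.
- Assumption, because actual enrollment dates are not given: the first subject entered 0 to 12 months after the original protocol date of 05-DEC-2014.
- First-course dosing then ends between 05-SEP-2018 (0 months) and 05-SEP-2019 (12 months).
- Amendment 12, which updated the irAE table, is dated 20-MAY-2021, about 32 and 20 months later respectively.

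On the planned timeline, later exposure would be mainly second-course retreatment of up to one year (Section 7.1.5.2.1), and Section 5.10 lets subjects move to an extension study. Slower or later enrollment than assumed would narrow the gap.

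**The case against.** The strongest reply is that the two texts do not contradict each other. Section 5.6.1 says what to do if diarrhea persists; it does not say to withhold steroids before then. Its measures are suggestions, Section 5.5 leaves the final decision on supportive therapy to the investigator or the subject's primary physician, and Section 5.5.2 excepts steroids given for adverse event symptoms from its prohibition. A site that treats early therefore complies with both texts. Table 4 is itself headed as guidelines. It does not demand an immediate start, and it advises considering gastroenterology consultation and endoscopy.

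Most of this stands, and it limits the size of the point. The difference is between a stated duration condition and none, not between a week and zero days. But the reply covers only sites that choose to treat early. A site that waits in Grade 3 colitis can point to 5.6.1, where 7.1.2.1 sent it, and would still depart from Table 4.

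A reader might go further and infer that the protocol has no rule on which text governs. The documents do not support that. Table 4 opens with a general-instructions row whose content is not readable in the text reviewed, and a rule could sit there. No claim is made that a precedence rule is absent.

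**Conclusion.** The mismatch is real for Grades 2 and 3, and it is minor. Two bullets in 5.6.1 carry persistence conditions, of more than 3 days and more than 1 week, that the corresponding line of Table 4 does not. For Grade 4 the contrast is only with the general introduction.

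A reader might infer that the plan tells sites to leave life-threatening colitis untreated for a week, against an explicit instruction in Table 4. That is too strong: the Grade 4 steroid cell is unreadable, and 5.6.1 neither binds sites nor forbids earlier treatment. The blank cell may be a merged one, since the lower steroid cell is also blank for severe pneumonitis and nephritis, but that is inference and the point does not need it.

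The number of subjects affected is unknown and probably small. That judgment rests on the planned enrollment period and the assumed first-subject date.

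**What to change.** Delete the persistence condition from each of the two diarrhea/colitis bullets in 5.6.1, or replace both bullets with a reference to the diarrhea/colitis row of Table 4. Add Table 4 to the cross-reference in 7.1.2.1. Tell sites of the change.

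Do not add a general sentence that Table 4 governs the start of steroids for all immune-related events. For Grade 3-4 hyperthyroidism, 5.6.1 advises intravenous then oral corticosteroids, whereas the readable hyperthyroidism row of Table 4 lists only beta-blockers or thionamides. A blanket rule would conflict with that advice. The change should stay within diarrhea/colitis.

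The cost is a wording change to two bullets, one cross-reference and a site letter. Data collection and analysis are unaffected.
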